3.4.3 Exploratory Efficacy Endpoint(s) and Analyses

3.4.3.1 Exploratory Efficacy Endpoint(s)

A 9x9 grid of black bars on a white background. The bars are arranged in a pattern where the width of each bar in a row increases from left to right. The first row has 1 bar, the second row has 2 bars, the third row has 3 bars, and so on, up to the ninth row which has 9 bars. The bars are separated by thin white gaps.

3.4.3.2 Exploratory Efficacy Analyses

The exploratory efficacy analyses with the ITT population will be performed using an analysis of covariance (ANCOVA) model adjusting for baseline value and treatment group. The analyses will be performed as well as analyzed separately for each part.

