^k Following a minimum 14 hr fast, a MMTT will be performed at 0800 \pm 15 min on Day -1; baseline blood samples will be collected at T = 0 (alongside samples for other blood tests and 2 H labelled glucose); a standardised liquid meal co-administered with C-13 labelled glucose (as required) will be given to subjects and consumed in entirety within 5 min. Further blood samples for glucose levels will be collected at T = 15, 30, 45, 60, 120, 180 and 220 min (\pm 5 min). Note that the start time of the MMTT may be adjusted to 1 hr before or 1 hr after provided all other related procedures are performed at the same time intervals.

^l MRS scans will be performed on Day -1 at 0700, 1200, 1700 and 2200 (\pm 15 min) and on Day 1 at 0800 (\pm 15 min). Note that times may be adjusted to 1 hr before or 1 hr after provided all other related procedures are performed at the same time intervals.

^m AEs will be assessed from the start of investigational product administration; SAEs will be assessed from the time of signed informed consent form.

ⁿ Subcutaneous injection training may be performed with saline prior to Day 1 and with the investigational product on Day 1; subjects should be provided with as much training as they need to be comfortable with SC self-injection between Day -3 through Day 1.

^o On Day -1 or Day 1, subjects will be randomised to receive investigational product: MEDI0382 or placebo. Subjects enrolled in Part A will not be re-enrolled in Part B.

^p A glucose meter, test strips, and a diary should be provided to the subject. The subject should be trained in its use and advised to test their capillary blood glucose at any time the subject feels unwell or has symptoms of hypoglycaemia (hunger, dizziness, shaking, sweating, or irritability) and they should record these symptoms and a capillary plasma glucose level in their diary only when symptomatic. Subjects should do this until their final study visit and bring the diary card with them to their next visit if they recorded symptoms or capillary plasma glucose levels while at home.

**Table 7 Schedule of Treatment Period Study Procedures (Day -4 through Day 15)
(Part A)**

Study Period	Outpatient	Baseline Measurements					Treatment Phase		
		V2					V3	V4	
Visit Number		Inpatient					Outpatient		
		Day -4	Day -3	Day -2	Day -1	Day 1 ^a	Day 8	Day 15	

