4.8 Statistical Evaluation

4.8.1 General Considerations

Tabular summaries will be presented by treatment group. Categorical data will be summarised by the number and percentage of subjects in each category. Continuous variables will be summarised by descriptive statistics. The study objectives will be evaluated on Part A and Part B separately and also on the combined cohorts as appropriate. Additional details of statistical analyses will be described in the statistical analysis plan.

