2.3 Treatment Assignment and Blinding

An IWRS will be used for randomization to a treatment group and assignment of investigational product kit numbers. A subject is considered randomized into the study when the IWRS provides the assignment of the subject's investigational product kit number.

Eligible subjects will be randomized at a 1:1 ratio following screening to receive either blinded MEDI0382 SC or placebo SC (Part A) or randomized at a 1:1:1 ratio following screening to receive either blinded MEDI0382 SC or placebo SC or open-label liraglutide SC (Part B). The IWRS will assign a unique randomization code and treatment group to the subject at the time of randomization. Subjects who withdraw from the study may be replaced, if deemed necessary by the medical monitor, to ensure that safety data are collected on a sufficient number of subjects.

In Part A only, this is a double-blind study in which MEDI0382 and placebo [REDACTED] [REDACTED] Neither the subject nor any of the investigator or sponsor staff who are involved in the treatment or clinical evaluation of subjects will be aware of treatment received.

[REDACTED] To maintain the blind in Part A of the study, investigational product (MEDI0382 and placebo) prefilled syringes will be handled by an unblinded investigational product manager or unblinded study personnel who will not be involved in the treatment or clinical evaluation of subjects. An unblinded site monitor will perform investigational product accountability, and this will be a different person from the blinded site monitor who will oversee other aspects of the study at the clinical site.

[REDACTED]. Each subject will know the volume of investigational product they have been instructed to select and administer, the subject and site staff are blinded with respect to whether they are receiving MEDI0382 or placebo. Liraglutide used in Part B will be open-label.

The site will maintain a written plan detailing which staff members are blinded/unblinded and the process of investigational product administration used to maintain the blind.

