3 STATISTICAL METHODS

3.1 General Considerations

In the event that there is a delay in data delivery or the full set of results is not expected to be available in timely manner (for example; follow-up of positive ADA results at 3 and 6

months after the follow-up visit) an initial database lock in Part B for the purpose of clinical study analysis and reporting will be performed when the last randomized subject completes the final visit or is discontinued prior to that visit. Final database lock will occur once all results have been received in the database.

In the event that an initial DBL is required, results received after this point may be reported in the clinical study report addendum.

Data will be presented in data listings sorted by study part, treatment, subject number and date collected, where appropriate. Tabular summaries will be presented by study part and treatment. Categorical data will be summarized by study part and treatment with the number and percentage of subjects within each category. In general, continuous variables will be summarized by study part and treatment with descriptive statistics including mean, standard deviation, median, minimum, and maximum. For some variables, the geometric mean and 95% CI may be presented.

All available data will be included in the analyses and missing data will not be imputed except as specified in the calculation of the AUC values. Unless specified otherwise, baseline values will be defined as the last valid assessment prior to the first administration of study medication.

The study objectives will be evaluated with analyses that include data from both Part A and Part B, if Part B is conducted. Analyses will also be performed separately for each study part. In general, the efficacy analyses will be analyzed with the ITT population and all other analyses will be performed with the As-treated population.

All statistical tests will be 2-sided at an alpha = 0.1 significance level unless stated otherwise. There will be no adjustment for multiplicity.

Data analyses will be performed using SAS[®] version 9.3 or higher (SAS Institute Inc., Cary, NC) in a UNIX environment.

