3.4.2.2 Secondary Efficacy Analyses

The secondary efficacy analyses will be performed using the ITT population.

The percentage change in fasting hepatic glycogen concentration (measured by MRS, adjusted for liver volume) at T = 24 hours post standardized morning meal from baseline (Day 1) to the end of 35 days of treatment, will be compared between MEDI0382 and liraglutide groups only in Part B of the study. This will be done using the ANCOVA model adjusting for baseline value and treatment group. A similar analysis will be applied to measure change in hepatic fat fraction from baseline (Day -1 or Day 1) to the end of 35 days of treatment (Day 35 or 36) versus placebo (Part B only).

The percentage change in fasting glycogen concentration (measured by MRS, adjusted for liver volume) at T = 24 hours post standardized morning meal from baseline (Day -1) to the end of 28 days of treatment, will be compared between MEDI0382 and placebo groups only in Part A of the study. This will be done using the ANCOVA model adjusting for baseline value and treatment group. A similar analysis will be applied to measure change in hepatic fat fraction from baseline (Day -1) to the end of 28 days of treatment versus placebo (Part A only).

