3.5.1.2 Exploratory Pharmacodynamic Analysis

The exploratory efficacy analyses will be performed using an analysis of covariance (ANCOVA) model adjusting for baseline value and treatment group. The analyses will be performed only separately for each part.

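### Models that combine Part A and Part B have no study-part term: MEDI0382 versus placebo becomes conservative, and any liraglutide contrast taken from them absorbs about half of any difference between the parts

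*SAP*

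**What the plan says.** SAP 3.1 states: "The study objectives will be evaluated with analyses that include data from both Part A and Part B, if Part B is conducted". Analyses by part are planned as well. Protocol 4.8.1 agrees, with a qualifier: objectives are "evaluated on Part A and Part B separately and also on the combined cohorts as appropriate". SAP 2.2 also reasons about Part B in terms of the sample size of the two parts taken together.

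For exploratory efficacy, SAP 3.4.3.2 specifies this model: "analysis of covariance (ANCOVA) model adjusting for baseline value and treatment group. The analyses will be performed as well as analyzed separately for each part". The second sentence is incomplete as it stands. The parallel sentence for pharmacodynamics in SAP 3.5.1.2 reads "The analyses will be performed only separately for each part", so the natural reading of 3.4.3.2 is combined as well as separate.

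Every ANCOVA in the SAP (3.4.1.3, 3.4.2.2, 3.4.3.2, 3.5.1.2) has two terms: baseline value and treatment group. SAP 2.3 describes two separate randomisations: 1:1 to "either blinded MEDI0382 SC or placebo SC (Part A) or randomized at a 1:1:1 ratio following screening" to MEDI0382, placebo or open-label liraglutide in Part B.

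The secondary liraglutide glycogen test in SAP 3.4.2.2 "will be compared between MEDI0382 and liraglutide groups only in Part B of the study". The visible text of 3.4.3.2 carries no such limit.

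**The concern.** Treatment was randomised within each part, not across parts. MEDI0382 and placebo occur in both parts and liraglutide in one. A combined model without a part term therefore compares a MEDI0382 group drawn about half from Part A with a liraglutide group drawn wholly from Part B. The Part A share of that comparison is not randomised, and any part-to-part difference in mean response enters the contrast.

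The parts differ by design:

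- Treatment lasts 28 days in Part A and 35 in Part B.
- The dose steps differ.
- Part A uses prefilled syringes and Part B a multidose pen.
- The postprandial scan is at 4 hours in Part A and 5 hours in Part B.
- Part A's meal footnote in Protocol Table 7 allows "a standardised liquid meal co-administered with C-13 labelled glucose (as required) will be given to subjects"; Part B's footnote in Table 9 does not mention C-13 glucose.
- One or more sites are planned for Part A and three or more for Part B.

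SAP 3.1 tests at a two-sided 0.10 level with no multiplicity adjustment. A part difference could therefore be reported as a difference between MEDI0382 and liraglutide. For MEDI0382 versus placebo the cost is precision, because the part difference goes into the residual.

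**Working it through.** **The plan's own figures.** These are the powers for MEDI0382 versus placebo in the Protocol synopsis, checked with a two-sample t-test (noncentral t).

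- Part A: difference 0.19 × 283 = 53.77, SD 41, 8 per arm, two-sided 0.10. Noncentrality = 53.77 / (41 × √(2/8)) = 2.62. Power is 0.802, against about 80% stated.
- Part B: difference 24.2, SD 17.0, 10 per arm, two-sided 0.05. Noncentrality = 24.2 / (17 × √(2/10)) = 3.18. Power is 0.853, against more than 80% stated.

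Both reproduce. The visible text gives no figure for a combined analysis or for MEDI0382 versus liraglutide.

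**Inputs for the combined model.** Part A randomises up to 20 at 1:1, so 10 MEDI0382 and 10 placebo. Part B randomises about 30 at 1:1:1, so 10 in each of three arms. The level is two-sided 0.10. Three inputs are assumptions, because the documents do not give them: an additive part shift of 0 to 1 SD, a baseline-outcome correlation of 0.3 or 0.5, and the same SD in both parts.

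**Expected contrast without a part term.** Write δ for the Part A minus Part B shift. The MEDI0382 mean contains (10/20)δ and the liraglutide mean contains none of it.

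- MEDI0382 − liraglutide = treatment difference + 0.5δ. With 8 Part A completers per arm the factor is 8/18 = 0.44.
- MEDI0382 − placebo = treatment difference + (10/20 − 10/20)δ, so no bias at balanced numbers. With, say, 7 MEDI0382 and 10 placebo completers in Part A, the factor is 7/17 − 10/20 = −0.09.

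On the Part B scale (SD 17 percentage points), a 0.5 SD shift moves the liraglutide contrast by 0.5 × 0.5 × 17 = 4.25 points, and a 1 SD shift by 8.5 points.

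**Rejection rates with no true treatment effect.** These come from simulated ANCOVA at nominal 10%, with 6,000 to 8,000 trials per setting. Ranges cover repeated runs and the two assumed correlations.

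| Assumed part shift | MEDI0382 − liraglutide, no part term | Same contrast, part term |
|---|---|---|
| 0 | about 10% | about 10% |
| 0.25 SD | about 12% | about 10% |
| 0.5 SD | 16-18% | about 10% |
| 1 SD | 30-35% | about 10% |

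With 8 Part A completers per arm and a 0.5 SD shift, the rate without a part term is 15%. For MEDI0382 − placebo without a part term, the rate at a 1 SD shift is about 7%. Power for an assumed 0.8 SD effect is then 78%, against 83% with the part term.

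**Precision of the liraglutide contrast.** Variance is in units of the residual variance, ignoring the baseline adjustment. Power is for an assumed 0.8 SD effect with no part shift.

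- Combined, no part term: 1/20 + 1/10 = 0.150; power about 67%.
- Combined with part term: the additive fit for MEDI0382 in Part B has variance 3/40, so 3/40 + 1/10 = 0.175; power about 62%.
- Part B only: 1/10 + 1/10 = 0.200; power about 55%.

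**The case against.** The strongest reply is that no section writes out a combined MEDI0382-liraglutide test. SAP 3.4.3.2 names no contrast, its key sentence is defective, and the exploratory endpoints are redacted, so a part restriction could sit in text that cannot be read. The Protocol combines parts only where appropriate, and its section 4.8.3.3 makes formal exploratory modelling optional. All of this stands, and it limits the point to what would follow if the model is run as written.

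A reader might go further and infer that the trial's main comparison with a GLP-1 mono-agonist is confounded. The documents do not support that. The one named liraglutide comparison is the secondary glycogen endpoint, and SAP 3.4.2.2 keeps it within Part B. Both primary analyses and the fat-fraction analyses are specified by part, and the pharmacodynamic analyses are run only by part.

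A reader might also infer that the parts used different sites. Protocol 4.1.1 gives only planned numbers of sites.

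The size of the shift is also open. Outcomes are changes from a baseline measured under the same part's conditions, so stable site or scanner offsets would largely cancel, and the scans at 0, 14 and 24 hours are common to both parts. At 0.25 SD the inflation is small. Duration, titration and device would mainly alter the MEDI0382 response itself. That is a treatment-by-part interaction, which a part term does not remove. This last objection is correct, and it is why the fix needs the Part B restriction as well as the term.

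**Conclusion.** The point holds in a limited form. Combined analyses are planned, the only model given leaves out the factor within which treatment was randomised, and a better model costs almost nothing.

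For MEDI0382 versus placebo, the effect is a conservative test when the parts differ, and no bias while numbers stay balanced across parts. For a MEDI0382-liraglutide contrast taken from the combined exploratory model, about half of any part shift is added to the treatment difference. The factor of one half follows from the planned numbers. The error rates rest on assumed additive shifts, since the documents give none, and there is no bias if the true shift is zero. The contrast is inferred from SAP 3.1 and 3.4.3.2, and the endpoints it would touch cannot be seen. This is a cheap improvement to exploratory analyses, not an error in a named confirmatory test.

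**What to change.** Complete the sentence in SAP 3.4.3.2 so that it says whether the exploratory efficacy analyses are run on the combined parts as well as by part. In SAP 3.1 and 3.4.3.2 add wording such as: *Every model that combines Part A and Part B includes study part as a fixed factor, with baseline value and treatment group. All comparisons with liraglutide use Part B subjects only.* Leave the part-specific models as they are.

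The Part B restriction is needed in addition to the term, because a part term alone does not correct for a MEDI0382 effect that differs between the parts.

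The cost is a sentence or two, one model term and one residual degree of freedom. With no part shift, power for MEDI0382 versus placebo is unchanged (82% with or without the term, assumed 0.8 SD effect). The liraglutide contrast gives up the precision borrowed from non-randomised Part A subjects: power falls from about 67% to about 55% with Part B only.

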3.5 Pharmacodynamic Analyses

3.5.1 Exploratory Pharmacodynamic Endpoint(s) and Analyses

3.5.1.1 Exploratory Pharmacodynamic Endpoint(s)

• [REDACTED]

Country	Percentage (2010)
United States	13%
United Kingdom	21%
Germany	21%
France	20%
Italy	19%
Spain	18%
Canada	17%
Australia	16%
New Zealand	15%
Japan	15%

3.5.1.2 Exploratory Pharmacodynamic Analysis

The exploratory efficacy analyses will be performed using an analysis of covariance (ANCOVA) model adjusting for baseline value and treatment group. The analyses will be performed only separately for each part.

3.6 Safety Analyses

3.6.1 Adverse Events and Serious Adverse Events

Adverse events will be coded with MedDRA version 21.0 or higher. Analysis of adverse events will include the type, incidence, severity and relationship to study investigational product summarized by MedDRA System Organ Class (SOC) and Preferred Term (PT) by study part treatment group as well as for combined study parts. The AEs summaries will include only treatment-emergent AEs, ie, those occurring after initial administration of investigational product. Subjects will be counted once for specific PT or MedDRA SOC when calculating incidence rates. If the same AE Preferred Term occurs multiple times within a subject, the highest severity and level of relationship observed will be reported. Non-treatment-emergent AEs/serious adverse events (SAEs) will be presented in the listings.

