1.3 Summary of Nonclinical Experience

1.4 Summary of Clinical Experience

Prior clinical studies with MEDI0382 have included a single ascending dose study (D5670C00001) in healthy subjects, and a multiple ascending dose and a Phase 2a study (D5670C00002) conducted in obese and overweight subjects with T2DM. In the Phase 2a study (Cohort 4 of Study D5670C00002), treatment with MEDI0382 at 200 µg (up titrated from a starting dose of 100 µg for 41 days with 2 titration steps of 4 days duration) was associated with a mean reduction from baseline in body weight of 4.1% (90% confidence interval [CI] -4.5, -3.4) in MEDI0382-treated subjects versus 1.8% (90% CI -2.5, -1.0) in placebo, $p < 0.001$, and a mean reduction from baseline in glucose AUC_{MMT.4h} of 32.8% (90% CI -37.0, -28.6) vs 10.2% (90% CI -14.1, -6.2) in placebo, $p \leq 0.0001$. While a reduction in blood glucose area under the concentration-time curve (AUC) is also anticipated in this study, given the difference in baseline subject characteristics (eg, metformin washout) and the higher carbohydrate content of the mixed-meal tolerance test (MMTT) assessment in this study, it is expected that the magnitude of AUC glucose reduction will be different.

MEDI0382 was also shown to have an acceptable safety profile in Study D5670C00002. There were no unexpected safety signals and no increases in systolic or diastolic BP across the study. In Cohort 4, dosing over 41 days was associated with increased gastrointestinal (GI) adverse events (AEs) with 40 AEs of vomiting observed in 8 (32%) subjects; however, the number of events diminished in frequency with up-titration (N = 19 at 100 µg, N = 10 at 150 µg, and N = 11 at 200 µg). The rates of nausea and vomiting were further reduced by lengthening the interval between titration steps to 5 days in Cohorts 5 and 6 of the same study dosing up to a dose level of 300 µg.

Refer to the current MEDI0382 IB for a complete summary of clinical information.

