4.8.4 Safety

4.8.4.1 Analysis of Adverse Events

Treatment-emergent AEs and SAEs will be summarized by type, incidence, severity and relationship to investigational product by system organ class (SOC) and preferred term (PT). Adverse events will be coded using the Medical Dictionary for Regulatory Activities (MedDRA). Specific AEs will be counted once for each subject for calculating rates, but will be presented in total in subject listings. In addition, if the same AE occurs multiple times within a particular subject, the highest severity and level of causality will be reported. If any associations of interest between AEs and baseline characteristics are observed, additional stratified results may be presented. All treatment-emergent AEs will be summarized overall and by MedDRA SOC and PT, by severity and relationship to investigational product. In addition, summaries of deaths, SAEs, and treatment discontinuations due to AEs will be provided.

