9.2 Protocol Amendment 5, 03May2019

Based on the analysis of data from Part A of this study, changes to Part B have been made to improve tolerability while still evaluating efficacy. The introduction of a multi-dose pen device to administer the investigational product facilitated the introduction of 50 μ g starting dose but this has had an impact on the duration of dosing. Formatting changes have also been made in line with the current process of the sponsor.

Changes relating to Part B of the study have been made in Protocol Amendment 5 and are summarized below. Other minor editorial changes have also been made.

Section Changed	Key Details of the Amendment
Amendment 5 / 03May2019	
Section 1.7 (Research Hypothesis), Section 2.1 (Primary Objective and Associated Endpoints), Section 2.2 (Secondary Objective and Associated Endpoints), Section 2.3 (Exploratory Objective and Associated Endpoints), Section 3.2.3.1 (Primary Endpoint),	
 Change in the primary endpoint to % change in fasting glycogen (at T = 24 hrs time point) Change in MRS schedule from 0, 4, 9, 14, and 24 hrs to 0, 5, 14 and 24 hrs Addition of analysis of endpoints are Day 35 for Part B
Section 3.1.1 (Overview), Section 3.1.2 (Treatment), Section 3.1.3 (Dose Escalation), Table 1, Section	
 The dosing schedule for MEDI0382 will now commence at a lower start dose of 50 μg and will be uptitrated in 7-day intervals to 300 μg

Section Changed	Key Details of the Amendment
3.2.3.3 (Exploratory Endpoints), Section 4.5 (Investigational Products), Section 4.8.3 (Efficacy)	
across 35 days; the end of treatment assessments have been altered to reflect this.
 
 The delivery device for MEDI0382 will be a pen device rather than PFS Introduction of a 14 hour fast prior to measurement of the scans related to the primary endpoint Alteration to visits; one less outpatient visit and two additional remote contacts to guide dose titration and collect AEs/SAEs.
Section 3.1.1 (Overview), Section 4.1.1 (Number of Subjects), Section 4.8.2 (Sample Size)	
 The number of subjects for Part B has increased to 30 (maximum 35 subjects)

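### The AE summaries specified in the SAP and protocol cannot show whether GI events recur or when in the titration they start; an events column and one onset-period table would add this

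*SAP*

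**What the plan says.** SAP 3.6.1 summarises treatment-emergent AEs by SOC and preferred term, severity and relationship, "by study part treatment group as well as for combined study parts". The counting rule is "Subjects will be counted once for specific PT or MedDRA SOC when calculating incidence rates". For repeats it adds: "If the same AE Preferred Term occurs multiple times within a subject, the highest severity and level of relationship observed will be reported".

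Protocol 4.8.4.1 has the same rule: "Specific AEs will be counted once for each subject for calculating rates, but will be presented in total in subject listings".

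Treatment-emergent means after the first administration, and SAP 3.6.1 sets no end. Protocol 5.3.1 collects AEs up to the visit 28 days after the last dose. Neither document names an event count, an exposure-adjusted rate, or a split by dose step or onset period for AEs.

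Protocol 1.4 reports vomiting in an earlier cohort differently: "40 AEs of vomiting observed in 8 (32%) subjects; however, the number of events diminished in frequency with up-titration". It then gives the count at each of three dose levels: 19, 10 and 11. Tolerability of MEDI0382 titrated to 300 µg is a secondary hypothesis (Protocol 1.7.2) and a secondary objective (Protocol 2.2). The rationale for Amendment 5 (Protocol 9.2) says "changes to Part B have been made to improve tolerability while still evaluating efficacy".

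**The concern.** GI events are the tolerability issue that the protocol itself raises, and it describes them by how often they recur and at which dose step. The specified AE tables carry neither dimension. An arm in which three subjects each vomit once in the first week gives the same incidence line as an arm in which three subjects vomit repeatedly at the top step.

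What is at stake is how well the trial can describe tolerability across titration, which is a stated secondary objective. The primary and secondary glycogen analyses are not affected.

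**Working it through.** **1. Reproduce the protocol's figures (Protocol 1.4).**
- Events by step: 19 + 10 + 11 = 40, as stated.
- Denominator: 8/n rounds to 32% only at n = 25, so 25 subjects.
- Events per affected subject: 40/8 = 5.0. Events per treated subject: 40/25 = 1.6.
- Share by step: 19/40 = 47.5%, 10/40 = 25%, 11/40 = 27.5%.

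**2. Apply the SAP rule to those figures.** Incidence = subjects with at least one event / subjects treated.

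| Vomiting events in the same 8 of 25 subjects | Incidence line | Events per treated subject |
|---|---|---|
| 8 | 8/25 = 32% | 0.32 |
| 20 | 32% | 0.8 |
| 40 | 32% | 1.6 |
| 80 | 32% | 3.2 |

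The incidence line does not change over a tenfold range of events. With no period column, it also cannot show the 19/10/11 split.

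**3. Illustrate the timing.** Protocol 1.4 gives 41 days with two titration steps of 4 days. Two assumptions are needed: a split of 4, 4 and 33 days, and all 25 subjects on dose throughout.
- First step: 19/(25 × 4) = 0.19 events per subject-day.
- Second step: 10/(25 × 4) = 0.10.
- Third step: 11/(25 × 33) = 0.013.
- Ratio of first to third: (19/4)/(11/33) = 14.25.

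If instead all 41 days were at the top step, the ratio is (19/4)/(11/41) = 17.7. These figures come from another study with another schedule. They show what a once-per-subject table hides, and they do not predict this trial.

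**4. Can the split be made from planned data?** The administration footnotes to Protocol Tables 7 and 9 fix the titration days.

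| | Planned periods |
|---|---|
| Part A, MEDI0382 | Days 1-7, 8-14, 15-28 |
| Part B, MEDI0382 | Days 1-7, 8-14, 15-21, 22-35 |
| Part B, liraglutide | Days 1-7, 8-14, then one level from Day 15 |

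Dose reduction is not permitted (Protocol 3.1.3), so the onset date gives the planned step for a subject still on treatment. Day 22 is not a dose step for liraglutide. The two parts have different steps, so their step tables cannot be pooled.

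**5. Is a denominator available?** SAP 3.3.3 summarises the number of doses and total dose by study part. It does not give time at each step, so days on treatment per period would have to be derived.

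**The case against.** The strongest reply is that this is only a matter of presentation, and much of that reply stands.

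- Counting a subject once per term is the ordinary incidence convention. A reader might infer that the rule is wrong; it is not.
- A reader might infer that the pattern is lost. It is not: repeat events go to subject listings (Protocol 4.8.4.1), sorted by part, treatment, subject and date (SAP 3.1). With about 10 subjects per arm, the pattern could be recovered by hand.
- It cannot be said that no table will show the pattern. SAP section 1 puts table templates in a statistical programming plan that is not among the documents. The claim reaches only what the SAP and protocol text require.
- A reader might infer that tolerability cannot be judged at all. That goes too far. Severity and relationship (SAP 3.6.1), discontinuations due to AEs (SAP 3.6.2), doses received (SAP 3.3.3) and concomitant medications, which would include antiemetics (SAP 3.3.4), all bear on it. None of these is specified to show recurrence or timing.
- A new table would not show that the changed titration works. Parts A and B are not randomised against each other, and they differ in device and duration. Within an arm, dose step is confounded with time on drug.
- No tolerability objective against liraglutide is stated, and that arm is open-label.
- The 28 days of follow-up do not dilute an ever/never proportion, because event-free days do not lower it. The reason to separate them is clarity about when events start.
- Cells will be sparse. Even 3 of 10 subjects has a 95% Clopper-Pearson interval of 6.7% to 65.2%, and single periods will hold fewer.
- The documents do not say whether repeat episodes are recorded as separate AEs or as one AE with a duration, so event counts depend on site recording.

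What remains is that neither text requires a summary showing recurrence or timing, although the protocol uses both to describe the drug's known GI effects.

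**Conclusion.** The point holds as a gap in specification and a cheap improvement, not as an error. The specified AE summaries run from first dose through follow-up with no period split; that reading rests on the absence of any stated window. On the protocol's own earlier data they would show 8/25 (32%) and omit the 40 events and their 19/10/11 split. The step-to-step contrast in daily rate, about 14-fold to 18-fold, rests on the assumed days per step and on full retention, and serves only as illustration.

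The documents do not support the stronger readings that the counting rule is faulty, that the data are lost, that tolerability is unassessable, or that a step table would isolate the effect of the new titration or support a planned tolerability contrast with liraglutide.

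**What to change.** In SAP 3.6.1, keep the incidence table and make two additions for nausea, vomiting and the GI disorders SOC.

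1. Show the number of events beside the number of subjects.
2. Add one table, by study part and arm, of subjects with onset and number of events by planned onset period:
   - Part A: Days 1-7, 8-14 and 15-28.
   - Part B: Days 1-7, 8-14, 15-21 and 22-35.
   - For placebo and liraglutide, label these as study-day periods, since liraglutide has no step at Day 22.
   - Use subjects and days actually on treatment in each period as the denominator, so that a subject who stops early leaves the later periods.
   - Show events after the last dose in a separate row.

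Do not pool the two parts' step tables. State in the SAP that the table is descriptive, that dose step is confounded with time on drug, that event counts depend on how repeat episodes are recorded, and that no effect of the titration change is inferred.

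The cost is one SAP paragraph and one table from onset and dosing dates. The downside is small counts per cell. This changes reporting only, not any dose or clinical rule.
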